The signature below constitutes agreement with this protocol and attachments, and provides assurance that this study will be conducted according to all stipulations of the protocol, including all statements regarding confidentiality, and according to national and local legal and regulatory requirements and applicable regulations and guidelines.

Principal Investigator:	
Address:	
Signature:	
Date:	

BTRX-335140	BlackThorn Therapeutics, Inc.
Clinical Study Protocol Amendment 7	Date: 24Jan2022

SUMMARY OF CHANGES

This section describes significant changes made in Version 8.0 of the protocol. Changes to punctuation, formatting (ie, changes in numbering, word order, location, etc.), the table of contents, and the list of abbreviations and definitions of terms are not listed in the summary of changes table (Table 1).

Section Number and Title	Description of Change	Rationale
Synopsis – Statistical Methods, Section 9 Statistical Considerations, Efficacy Analyses	Changed alpha, power, and confidence interval (CI) for efficacy analyses to reflect 2-sided alpha=0.05; power of 84% and 95% CIs	To decrease the chance of a Type I error.
Synopsis – Study Design, Schedule of Procedures and Assessments (footnotes c, h, and t), Section 3.1, Section 6.3.6, Section 7.6, Section 7.7.2, Section 7.8	Clarified wording around the Week 12 corneal specular microscopy, which should be completed for all subjects (ie, completers and early termination) unless consent is withdrawn. Also added clarification that additional ophthalmologic examinations (standard ophthalmologic exams and/or corneal specular microscopies) may be conducted at any time during the study to assess subject safety.	In the event of early termination, every attempt should be made to get a subject to come back for corneal specular microscopy at 12 weeks after the first dose of study drug. Added text to reflect potential of unscheduled ophthalmologic and/or corneal specular microscopies to assess safety
Section 3.2.2, Section 3.2.3, Section 9.3.3.2, Section 9.3.5	Moved CGI-S from an exploratory to a secondary endpoint.	Supports the secondary objectives; consistency with the SAP
Synopsis – Statistical Methods, Section 9.3.3.2	Added description for analysis of CGI-S using generalized estimating equations (GEE)	Consistency with the SAP
Synopsis – Statistical Methods, Section 9.3.3.2	Revised statistical text for secondary efficacy analyses to allow for ANCOVA as appropriate.	Clarity and consistency with the SAP

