Subjects who meet the DSM-5 diagnostic criteria for MDD and all other eligibility criteria for the study will be randomized in a 1:1 ratio to 1 of 2 treatment arms (placebo or BTRX-335140 QD) until approximately 180 subjects are randomized. Beginning at Visit 2 (Baseline), subjects will receive treatment with BTRX-335140 80 mg QD or placebo for 8 weeks. During the Safety Follow-up, all subjects will receive a telephone call (TC) from study site personnel approximately 2 weeks after discontinuation of study drug for assessment of AEs, concomitant medication usage, and C-SSRS; and at Week 12, subjects will have corneal specular microscopy performed by a study site-affiliated ophthalmologist. The overall duration in the study for each subject is expected to be approximately 14 to 16 weeks.

The Week 12 corneal specular microscopy should be completed for all subjects (ie, completers and early termination) unless consent is withdrawn. The corneal specular microscopy should be conducted approximately 12 weeks after the first dose of study drug; subjects who terminate the study early would need to plan for the corneal specular microscopy at 12 weeks after the first dose of study drug. Any exceptions are to be discussed with the medical monitor.

Additional ophthalmologic examinations (standard ophthalmologic exams and/or corneal specular microscopies) may be conducted to assess subject safety.

Details of study procedures and assessments are provided in Section 6; for details on the timings of study assessments refer to Section 7 and the Schedule of Procedures and Assessments.

Study sites will maintain, at a minimum, coronavirus disease 2019 (COVID-19) risk mitigation procedures as per regulatory and local guidelines and/or laws. Allowed modifications to the conduct of the study, in the event of site staff and/or patient restrictions due to COVID-19, are outlined in Appendix 1.

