9 STATISTICAL CONSIDERATIONS

9.1 General Considerations

Full details on the statistical methodology to be used will be included in a statistical analysis plan (SAP) to be developed prior to study unblinding.

For the purpose of all safety analyses where applicable, baseline is defined as the last measurement prior to the start of study drug administration. For efficacy analyses, baseline is defined as the arithmetic mean of pretreatment measurements ie, Screening and Baseline, prior to the first administration of study drug, or as the last measurement prior to the first administration of study drug if only single value is available.

Continuous endpoints will be summarized with n, mean, standard deviation (SD), median, minimum and maximum. In addition, change from baseline and percent change from baseline values will be calculated at each time point and summarized descriptively. For categorical endpoints, descriptive summaries will include counts and percentages.

No adjustments will be made for multiple comparisons.

All statistical comparisons will be 2-sided with alpha of 0.05.

SAS version 9.4 or higher will be used to analyze data.

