9.3.3.1 Primary Efficacy Analysis

The primary efficacy analysis is a comparison of mean reduction in HAMD-17 scores between BTRX-335140 and placebo at Week 8. The analysis will be conducted using a Mixed-Models Repeated Measures (MMRM) with change from baseline in HAMD-17 score as the dependent variable and will include treatment group, Week, and Week by treatment group interaction as factors, and baseline HAMD-17 score as covariate. Variance estimation will be based on an unstructured covariance matrix. The model-based Week 8 least square (LS) means, standard errors, 95% confidence intervals (CIs), and *p*-values will be reported.

9.3.3.2 Secondary Efficacy Analyses

Similar to the method described above, a MMRM model will be calculated for the change from baseline to each timepoint assessed for comparisons between BTRX-335140 and placebo for the measures listed below. The model-based time points' LS means, standard errors, 95% CIs, and *p*-values will be reported. Alternatively, ANCOVA may be used, as appropriate. The following measures will be analyzed:

- CGI-I
- CGI-S
- SHAPS
- HADS subscales: HADS-A and HADS-D

BTRX-335140	
Clinical Study Protocol Amendment 7	

- HAM-A total score
- SDS

For CGI-I, an additional analysis comparing the percentage of subjects with responses at Week 4 and Week 8 of 'much improved' or 'very much improved' between BTRX-335140 and placebo will be performed using generalized estimating equations (GEE). The model will include treatment, baseline CGI-S score, week, and week by treatment group interaction. An exchangeable working correlation structure will be assumed.

The change from baseline to Week 8 in CGI-S will be estimated using an ANCOVA model, with main effects for treatment group and a covariate adjustment for baseline score.

The response rates (the percentage of subjects with \geq 50% decrease in HAMD-17 from baseline to Week 4 and Week 8) will be compared between BTRX-335140 and placebo-treated groups using Cochran-Mantel-Haenszel test. Additional categories may be explored.

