7.4.4 Primary Efficacy Endpoint Analysis Methods

The primary efficacy endpoint is the change from baseline to Week 8 on the HAMD-17 score. The estimand for the primary efficacy endpoint is the difference in means between treatment groups in the change of HAMD-17 scores from baseline to Week 8 for all subjects in the Efficacy population. For efficacy analyses, baseline is defined as the latest measurement prior to the first administration of study drug. The null hypothesis to be tested is that there is no difference between BTRX-335140 and placebo:

H₀:
$$\mu_A = \mu_{B_i}$$

Where μ_A and μ_B represent the mean values for BTRX-335140 and placebo, respectively. The alternate hypothesis to be tested is that the treatment group means differ:

H₁:
$$\mu_A \neq \mu_{B}$$
;

The analysis will be conducted using a mixed-models repeated measures (MMRM) with change from baseline in HAMD-17 score as the dependent variable and will include treatment group, week, and week by treatment group interaction as factors, and baseline HAMD-17 score as covariate. Variance estimation will be based on an unstructured covariance matrix. If the unstructured covariance matrix results in a lack of convergence, the heterogeneous autoregressive variance-covariance structure will be used.

The primary analysis will compare the groups at Week 8. The primary results obtained from the model will be the estimated treatment difference at Week 8. Significance will be assessed based on a two-sided test at the α =0.05 level of significance. In addition, the estimated treatment difference at Week 4 will be provided. The model-based least square (LS) means, standard errors, 95% CIs, and 2-sided p-values will be reported.

In addition, descriptive summary of HAMD-17 and each individual item will be generated by treatment group and by visit.

BlackThorn Therapeutics, Inc.	Statistical Analysis Plan
K2-MDD-201	Version 2.0; 03 June 2022

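### The primary MMRM fits one baseline HAMD-17 slope to Week 4 and Week 8; a baseline-by-week term is a cheap safeguard with a small and uncertain gain

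*SAP*

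**What the plan says.** SAP 7.4.4 models change from baseline in HAMD-17 with treatment group, "week, and week by treatment group interaction as factors, and baseline HAMD-17 score as covariate". Protocol 9.3.3.1 gives the same terms, ending "Week by treatment group interaction as factors, and baseline HAMD-17 score as covariate", and the protocol synopsis agrees. The covariance is unstructured, and the SAP adds a heterogeneous autoregressive fallback if the model does not converge. The primary result is the treatment difference at Week 8.

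The schedules in both documents, and the efficacy windows in SAP Table 3, place post-baseline HAMD-17 at Weeks 4 and 8 only. The treatment effect may therefore vary by week, while the baseline effect may not.

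SAP 7.4.7 uses the same form for SHAPS, HADS, HAM-A and SDS, each with its own baseline. CGI-I carries no baseline covariate. SAP addendum 5.2.3 repeats the primary model in every subgroup. SAP sections 4 and 7.7 state that nothing departs from the protocol's planned analyses.

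**The concern.** The fitted common slope is a weighted average of the two visit-specific slopes, and the weights come from the residual covariance. When Week 4 is less variable than Week 8 and the two are positively correlated, most of the weight falls on Week 4. If change at Week 8 depends more strongly on baseline than change at Week 4, the primary time point is adjusted with a slope that belongs mostly to the other visit.

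Two things are at stake. The first is precision: a wrong slope leaves some baseline-related variance in the Week 8 residual. The second is bias: subjects missing at Week 8 are in effect predicted from Week 4 and baseline, so a wrong slope matters if those who stay differ in baseline between the arms.

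**Working it through.** **Inputs from the documents.** Two-sided alpha is 0.05 ("All statistical comparisons will be 2-sided with alpha of 0.05", protocol 9.1). The protocol's Summary of Changes records "2-sided alpha=0.05; power of 84% and 95% CIs". Allocation is 1:1 "until approximately 180 subjects are randomized" (protocol 3.1), so about 90 per arm.

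**Inputs assumed, because the available text gives none.** Residual SD s4 = 5.5 at Week 4 and s8 = 7 at Week 8; residual correlation r from 0.5 to 0.75; baseline SD s0 from 2.5 to 4.5; slope difference d between Week 8 and Week 4 from 0 to 0.5 in size; Week 8 missingness 0% or about 20%.

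**The stated 84%.** It cannot be reproduced without the effect size and SD, which are not visible; this is not counted against the plan. At 90 per arm it implies a standardized effect of (1.960 + 0.994) × √(2/90) = 0.440, or 0.440 × 7 = 3.1 points if the SD is 7.

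**Weight on each visit, r = 0.65.** The common slope converges to 1'S⁻¹b / 1'S⁻¹1, where S is the residual covariance matrix and b holds the two slopes. For two visits the weight on Week 4 is

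w4 = (s8² − r·s4·s8) / (s4² + s8² − 2r·s4·s8) = (49 − 25.025) / (30.25 + 49 − 50.05) = 23.975 / 29.2 = 0.82,

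so w8 = 0.18. At r = 0.5 the Week 8 weight is 0.27; at r = 0.75 it is 0.06.

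**Precision, complete data, large sample.** The Week 8 variance ratio, common slope against slope by week, is 1 + (w4·d·s0)² / s8². For d = 0.2, s0 = 3.5 and r = 0.65: 1 + (0.821 × 0.2 × 3.5)² / 49 = 1 + 0.330/49 = 1.0067. The SE change is 1/√1.0067 − 1 = −0.34%. With power set to 84.0% under the planned model:

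| d | s0 | r | Variance ratio | SE change | Power with baseline-by-week |
|---|---|---|---|---|---|
| 0 | 3.5 | 0.65 | 1.000 | 0.00% | 84.0% |
| 0.1 | 3.5 | 0.65 | 1.002 | −0.08% | 84.1% |
| 0.2 | 3.5 | 0.65 | 1.007 | −0.34% | 84.2% |
| 0.3 | 3.5 | 0.65 | 1.015 | −0.75% | 84.5% |
| 0.5 | 3.5 | 0.65 | 1.042 | −2.0% | 85.5% |
| 0.5 | 4.5 | 0.75 | 1.091 | −4.2% | 87.0% |

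At s0 = 2.5 and r = 0.5, even d = 0.5 gives only −0.84%.

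**Precision, simulation.** REML fits of both models to the same data, 180 subjects, 800 runs per row, about 20% missing at random at Week 8:

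| d | s0 | Mean SE, planned | Mean SE, by week | Change | Runs where by-week SE is smaller |
|---|---|---|---|---|---|
| 0 | 3.5 | 1.119 | 1.121 | +0.19% | 22% |
| 0.1 | 3.5 | 1.116 | 1.117 | +0.04% | 36% |
| 0.2 | 3.5 | 1.123 | 1.119 | −0.33% | 60% |
| 0.3 | 3.5 | 1.132 | 1.122 | −0.87% | 82% |
| 0.5 | 4.5 | 1.174 | 1.124 | −4.2% | 99% |

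The two models' mean Week 8 estimates differed by at most 0.013 points. Null rejection was 4.0% (planned) against 4.1% (by week) at d = 0, and 5.0% for both at d = 0.3.

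**Bias when baseline-related dropout differs by arm.** Let g be the difference between arms in mean baseline among those observed at Week 8, in excess of any difference at randomization. With k = r·s8/s4 = 0.65 × 7/5.5 = 0.827, the common-slope bias at Week 8 is about d × (w4 + k·w8) × g = d × (0.821 + 0.827 × 0.179) × g = 0.97·d·g.

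- d = 0.2, g = 0.2: 0.04 points.
- d = 0.3, g = 0.5: 0.15 points.
- d = 0.5, g = 0.75: 0.36 points.

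Fitting both models to 400,000 simulated subjects with no treatment effect (d = 0.3, s0 = 3.5, r = 0.65, 21% missing, g = 0.96) gave 0.28 points under the planned model, against 0.28 from the formula, and 0.00 with baseline-by-week.

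**The case against.** The strongest case against is that nothing here is wrong. Protocol and SAP agree on a fully specified model with unstructured covariance and a week-by-treatment term. No passage gives a baseline SD, an outcome SD, a correlation or a slope, so the idea that change depends more on baseline at later visits has no support in the documents. If the slopes are equal or differ by 0.1, the extra term gains nothing or loses a trace. Eligibility also rests on a clinical-scale rule list whose content is not visible. It may narrow the baseline spread, and the gain scales with the square of that spread.

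All of this stands, and it limits the point. A reader might infer that the added term does sharpen the Week 8 comparison, or that Week 8 is under-adjusted as planned. Both hold only if the slopes differ, which the documents do not show. A reader might also infer that the planned test is invalid. The simulations do not support that: type I error was at its nominal level, and bias appeared only when unequal slopes were combined with dropout that depends on baseline differently by arm.

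What the objection does not remove is the asymmetry. The worst result in the simulations was a 0.19% larger SE. The gains, though uncertain, reach several percent, and the by-week model does not rely on equal slopes.

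**Conclusion.** A cheap improvement, not an error. It is certain that the plan forces one baseline slope on both HAMD-17 visits and that freeing it costs one parameter in the primary model. The benefit is conditional. The Week 8 SE goes from about 0.2% larger with equal slopes, through under 1% smaller at a difference of 0.2 to 0.3 (baseline SD 3.5), to about 2 to 4% smaller at 0.5 (baseline SD 3.5 to 4.5). In power, that is no gain at equal slopes, about 0.2 to 0.5 points in the middle of the range and about 3 points at the extreme. The bias it guards against is about 0.04 to 0.36 HAMD-17 points for the slope differences and baseline gaps shown, against an implied effect near 3.1 points if the SD is 7. Every SD, correlation, slope and dropout pattern used is an assumption.

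**What to change.** Before unblinding, add a baseline-by-week interaction to the primary MMRM in SAP 7.4.4, and to the MMRMs in SAP 7.4.7 that carry a baseline covariate: SHAPS, HAM-A, HADS and SDS. CGI-I is unaffected. The subgroup models in addendum 5.2.3 then follow.

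Record the change. The model is written out in the protocol synopsis and in 9.3.3.1, so this needs either a protocol amendment or a declared departure, and the no-changes statements in SAP sections 4 and 7.7 must be revised.

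The cost in parameters is the number of post-baseline visits minus one: one for HAMD-17, HAM-A and SHAPS (Weeks 4, 8), two for SDS (Weeks 4, 6, 8) and three for HADS (Weeks 2, 4, 6, 8). If the slopes are equal, the SE may rise trivially. If treatment codes have already been opened, keep the planned model as primary and report the by-week version as a labelled supplementary analysis.

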7.4.5 Sensitivity Analyses of the Primary Efficacy Endpoint

Sensitivity analyses will be used to investigate the impact of important protocol deviations or missing data for the primary efficacy endpoint assessment (ie, HAMD-17 total score). The primary efficacy analysis will be repeated using

- The per-protocol population.
- If ≥10% of subjects have missing data for the primary efficacy endpoint assessment (i.e., HAMD-17 total score), the following will be conducted:
 - Rubin's rules for multiple imputation (MI) with SAS Proc MI and MIANALYSIS for the efficacy population. See Appendix B : Steps for Multiple Imputation for further details.
 - Last Observation Carried Forward (LOCF) Imputation technique, ie, the last observed non-missing value will be used to fill in missing values at a later point in the study, regardless of when the missing value occurred. The imputed dataset generated with the LOCF technique will be used as input data in the ANCOVA. The efficacy population will be used.

7.4.6 Subgroup Analyses of the Primary Efficacy Endpoint

The primary efficacy endpoint (change from baseline to Week 8 in HAMD-17 total score) will be summarized using the following subgroups:

- Gender (male and female)
- Baseline HAMD-17 scores: $< 22 \text{ vs} \ge 22$
- by baseline SHAPS Total Score (14 to 56) (< median and ≥ median) and SHAPS Original Total Score (0 to 14) (< median and ≥ median).

Summaries by subgroup will only be produced if there are at least 20 subjects in the category of interest. Additional subgroup analyses may be performed post-hoc, as appropriate.

The primary endpoint (HAMD-17 total score) will also be summarized in subgroups of the Efficacy Population that include all subjects screened on or before March 16, 2020 (labeled as PreCOVID) versus the subjects screened after March 16, 2020 (labeled as PostCOVID).

7.4.7 Secondary Endpoint Analysis Methods

Secondary endpoints including the change from baseline to each timepoint assessed for comparisons between BTRX-335140 and placebo for the measures listed below, will be analyzed using an MMRM model for treatment group, week, and week by treatment group interaction as fixed factors and a covariate adjustment for baseline score. For CGI-I, the baseline CGI-I score will not be included as a covariate, as the baseline assessment of CGI-I refers to the comparison with screening visit. For all other measures the baseline score included as a covariate will be the baseline score for that measure. Variance estimation will be based on an unstructured covariance matrix unless there is a lack of convergence in which case a heterogeneous autoregressive variance-covariance structure will be used.

- CGI-I at each post-baseline visit
- Change in SHAPS from baseline at each post-baseline visit
- Change in HADS total score and HADS subscales: HADS-A and HADS-D from baseline at each post-baseline visit
- Change in HAM-A total score from baseline at each post-baseline visit
- Change in SDS from baseline at each post-baseline visit

The response rates (the percentage of subjects with \geq 50% decrease in HAMD-17 from baseline to Week 4 and Week 8) will be compared between BTRX-335140 and placebotreated groups. The response rates, response rate difference and corresponding 95% Wald CI, and Cochran-Mantel-Haenszel p-value will be reported.

The change at Week 8 from baseline in CGI-S will be estimated using an analysis of the covariance (ANCOVA) model with main effects for treatment group and a covariate adjustment for baseline CGI-S score. The model-based LS means, standard errors, 95% CIs, and 2-sided p-values will be reported.

For SDS, analysis will be performed for the three SDS items separately and the SDS total score as the sum of the individual domains. Note that the work/school domain may be not applicable for all subjects and therefore the analysis of SDS total score will be performed for the subjects with all 3 domain scores and the checkbox of "No work or school" is NOT marked. In addition, a sensitivity analysis of SDS total score will be conducted for all subjects, where the SDS total score will be calculated as (sum of social and family life)*30/20 for the subjects for whom the checkbox of "No work or school" is marked.

For CGI-I, an additional analysis will be performed to compare the symptom improvement rate, i.e. the percentage of subjects with responses at each post-baseline visit of 'much improved' or 'very much improved' (i.e. CGI-I score ≤2) between BTRX-335140 and placebo. The symptom improvement rate, improvement rate difference and corresponding 95% Wald CI, and Cochran-Mantel-Haenszel p-value will be reported.

BlackThorn Therapeutics, Inc.	Statistical Analysis Plan
K2-MDD-201	Version 2.0; 03 June 2022

For SHAPS, the analyses will be performed for the SHAPS total scores based on both methods of scoring (SHAPS Total Score [14 to 56] and SHAPS Original Total Score [0 to 14]).

In addition, descriptive summaries of each secondary efficacy variable will be generated by treatment group and by visit.

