Clinical Study Protocol Amendment 7	

All efficacy endpoints will also be summarized by visit, including change from baseline information.

Statistical Methods: All statistical comparisons will be made at a 2-sided alpha of 0.05. No adjustment for multiplicity is planned. SAS Version 9.4 or higher will be used to analyze data.

Subjects will be analyzed according to randomized treatment assignment for efficacy assessments and according to treatment received for safety assessments.

Primary Efficacy Analysis: The primary efficacy analysis is a comparison of mean reduction in HAMD-17 scores between BTRX-335140 and placebo at Week 8. The analysis will be conducted using a Mixed-Models Repeated Measures (MMRM) with change from baseline HAMD-17 score as the dependent variable and will include treatment group, Week, and Week by treatment group interaction as factors, and baseline HAMD-17 score as covariate. Variance estimation will be based on an unstructured covariance matrix. The model-based Week 8 least square (LS) means, standard errors, 95% confidence intervals (CIs), and *p*-values will be reported.

Secondary Efficacy Analysis: Comparisons between BTRX-335140 versus placebo for the change from baseline in score at each timepoint assessed for the secondary endpoints will be conducted using MMRM analyses as specified above or analysis of covariance (ANCOVA), as appropriate. For CGI-I an additional analysis comparing the percentage of subjects with responses of 'much improved' or 'very much improved' at each timepoint between BTRX-335140 and placebo will be performed using generalized estimating equations (GEE). Response rates for decrease in HAMD-17 (e.g., the percentage of subjects with \geq 50% decrease in HAMD-17 from baseline to Week 4 and Week 8) will be compared between BTRX-335140 and placebo using Cochran-Mantel-Haenszel tests.

Safety Analyses: Safety data, including AEs, safety laboratory results, physical examination results, vital signs, suicidality, COWS scores, ECGs, and ophthalmologic examination findings will be summarized by treatment group and/or listed.

BTRX-335140	
Clinical Study Protocol Amendment 7	

SCHEDULE OF PROCEDURES AND ASSESSMENTS

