5.1.2 Baseline Definition

For efficacy and safety analyses presented by study visit, the main SAP defines the baseline value as "the last measurement prior to the start of study drug administration". The baseline value will differ for summaries of Hamilton Depression Rating Scale - 17item Version (HAMD-17), Clinical Global Impression of Improvement (CGI-I), Snaith-Hamilton Pleasure Scale (SHAPS), Hospital Anxiety and Depression Scale (HADS), Hamilton Anxiety Rating Scale (HAM-A), Sheehan Disability Scale (SDS), Clinical Global Impression of Severity (CGI-S),

and

presented by study visit, in which case the baseline value will be defined as the last measurement prior to or within 1 hour of the first administration of study drug. For all other efficacy and safety analyses presented by study visit, the baseline value will be defined as stated in the main SAP.

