6.4.1.2 Secondary Efficacy Variables

Secondary efficacy endpoints include the following:

- HAMD-17 response rate at Week 4 and Week 8. The response rate is the percentage of subjects with \geq 50% decrease from baseline in HAMD-17 score.
- CGI-I. CGI-I score assessed at each postbaseline timepoint compared to baseline. The CGI-I scale (Guy 1976) is a clinician-rated instrument that measures the improvement of the subject's symptoms. It is a 7-point scale where a score of 1 indicates that the subject is "very much improved," a score of 4 indicates that the subject has experienced "no change," and a score of 7 indicates that the subject is "very much worse." For analysis purposes, a CGI-I response indicating symptom improvement will be defined as "much improved" or "very much improved".
- SHAPS. Change from baseline to each timepoint assessed in SHAPS scores. The SHAPS is a 14-item self-report instrument which measures anhedonia (Snaith et al 1995). Each of the 14 items has a set of 4 responses, 2 of which endorse agreement (Definitely/Strongly Agree, Agree) and 2 of which endorse disagreement (Disagree, Strongly Disagree). There are two scoring methods.
 - SHAPS Original Total Score (0 to 14): The original method assigned a score of 1 to either of the disagreement responses (Disagree, Strongly Disagree) and a score of 0 to either of the agreement responses (Definitely/Strongly Agree, Agree). Therefore, original scores on the SHAPS can range from 0-14 with higher scores corresponding to higher levels of anhedonia.
 - SHAPS Total Score (14 to 56): The second method derives a total score by summing the item responses where Definitely/Strongly Agree responses score 1 point, Agree responses score 2 points, Disagree responses score 3 points, and Strongly Disagree responses score 4 points. Therefore, scores on the SHAPS can range from 14 to 56 by the second method, with higher scores corresponding to higher levels of anhedonia. Both methods will be used for analyses.

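### The CGI-I repeated-measures model rightly omits the Visit 2 CGI-I but puts no baseline severity covariate in its place, although baseline CGI-S is available for the purpose

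*SAP*

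**What the plan says.** **The CGI-I model.** SAP 7.4.7 specifies one MMRM form for the secondary scales: treatment, week, their interaction, and an adjustment for baseline score. It makes one exception, which concerns CGI-I and reads: "the baseline CGI-I score will not be included as a covariate, as the baseline assessment of CGI-I refers to the comparison with screening visit". It then adds: "For all other measures the baseline score included as a covariate will be the baseline score for that measure". SHAPS, HADS, HAM-A and SDS are thus each adjusted for their own baseline, and no covariate is named for CGI-I. The outcome is listed as "CGI-I at each post-baseline visit", whereas the other items in that list are worded as changes.

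**Reference points.** SAP 6.4.1.2 describes the endpoint as "CGI-I score assessed at each postbaseline timepoint compared to baseline". The Visit 2 rating, by SAP 7.4.7, refers to screening.

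**Baseline CGI-S.** The Schedule of Procedures and Assessments and Protocol 7.2 have CGI-S rated at Visit 2, alongside CGI-I. In Protocol 9.3.3.2 the GEE for CGI-I responders already uses it: "The model will include treatment, baseline CGI-S score, week, and week by treatment group interaction".

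**Change from baseline.** The Protocol Synopsis says "All efficacy endpoints will also be summarized by visit, including change from baseline information". Protocol 9.1 says of continuous endpoints that "change from baseline and percent change from baseline values will be calculated at each time point and summarized descriptively". CGI-I also heads the list of measures that Protocol 9.3.3.2 analyzes as change from baseline. None of these places makes an exception for CGI-I.

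**The concern.** CGI-I measures improvement, so it has no baseline of its own in the usual sense. The usual substitute is a severity score taken at baseline, and CGI-S is the companion scale. The SAP sees that the Visit 2 CGI-I cannot play this role, removes it, and stops there.

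Two things are at stake, both modest. The CGI-I treatment contrast carries any outcome variance that baseline severity could explain, and it is left open to a chance difference in severity between arms. The other secondary MMRMs are adjusted for both.

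A separate question of wording follows from the two reference points. If a programmer takes the protocol's general instructions literally, a by-visit table would show CGI-I at Week 8 minus CGI-I at Visit 2. That difference has no clear meaning.

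**Working it through.** **1. The plan's own figure.** The documents give no SD, effect size or correlation for CGI-I. The nearest figure is the 84% power in the protocol's Summary of Changes, for the efficacy analyses in general. Its effect size and SD are not in the available text, so it cannot be reproduced, only inverted. With 180 subjects, 90 per arm, two-sided alpha 0.05 and no dropout:

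d = (1.960 + 0.994) × √(2/90) = 2.954 × 0.149 = 0.44

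This serves below only as a reference effect.

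**2. Bias.** Treatment is randomized 1:1, so leaving out a baseline covariate does not shift the expected difference. In 4,000 simulated trials per correlation (90 per arm, with and without the covariate) the mean estimates agreed within about 0.001.

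**3. Precision.** For one visit, adjusting for a covariate with correlation ρ multiplies the outcome variance by (1 − ρ²), so the SE falls by 1 − √(1 − ρ²). The equivalent sample size is 180/(1 − ρ²). Power is Φ(d√(n/2)/√(1 − ρ²) − 1.960) with n = 90. All values of ρ are assumptions.

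| ρ | SE reduction | Equivalent N | Power at d = 0.44 | Power at d = 0.30 |
|---|---|---|---|---|
| 0 | 0.0% | 180 | 84.0% | 52.1% |
| 0.1 | 0.5% | 182 | 84.4% | 52.5% |
| 0.2 | 2.0% | 188 | 85.4% | 53.7% |
| 0.3 | 4.6% | 198 | 87.2% | 55.9% |
| 0.5 | 13.4% | 240 | 92.7% | 64.2% |

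Example: at ρ = 0.3, 1 − √0.91 = 0.046 and 180/0.91 = 198. The simulated mean SE fell from 0.1490 to 0.1464 at ρ = 0.2 and from 0.1489 to 0.1424 at ρ = 0.3. At ρ = 0 it rose from 0.1486 to 0.1490, the cost of one degree of freedom. The formula is for a single visit; in the MMRM it applies approximately, if the CGI-S slope is similar across weeks.

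**4. Chance imbalance.** With 90 per arm, the standardized difference in baseline CGI-S between arms has standard error √(2/90) = 0.149. An imbalance of two standard errors is 0.298 SD. It would move the unadjusted CGI-I difference by ρ × 0.298: 0.03 SD at ρ = 0.1 and 0.09 SD at ρ = 0.3. Adjustment removes this shift.

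**5. Why a CGI-I change score has no clear meaning.** A score of 4 means no change. Take a subject rated 3 at Visit 2 (better than at screening) and 4 at Week 8 (no change since baseline). The change is 4 − 3 = +1, which reads as worsening although the rater recorded none. Two subjects both rated 2 at Week 8, with Visit 2 ratings of 3 and 4, get changes of −1 and −2 for the same recorded improvement since baseline.

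**The case against.** The case for leaving the model alone has force. CGI-I is already a rating relative to baseline, and the unadjusted comparison is unbiased. The gain depends on a correlation that the documents do not give, and at zero the SE rises very slightly. This is one of several secondary endpoints in a Phase 2a study with no multiplicity control. All of that stands, and it makes this a minor point.

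Three stronger readings are tempting, and the documents do not support them.

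- *A reader might infer that the planned CGI-I results are spoiled by mixed reference points.* The opening of SAP 7.4.7 does speak loosely of change from baseline, but its CGI-I item is the score at each visit. SAP 7.4.7 also asks only for descriptive summaries by treatment group and visit. Any extra variance from subtracting the Visit 2 rating would therefore reach no estimate, interval or p-value that the SAP plans. The call for a CGI-I change comes from the protocol's general wording.
- *A reader might infer that SAP addendum 5.1.2 creates the problem by listing CGI-I among measures with a baseline value, and that deleting it there would cure it.* The addendum only settles which record counts as baseline. Without that entry, CGI-I would revert to the main SAP's baseline definition in 7.1.5, and Table 3 would still give it a baseline window.
- *A reader might infer that every other secondary analysis is protected against severity imbalance.* The HAMD-17 response rate and CGI-I improvement rate are compared by a Wald interval and a Cochran-Mantel-Haenszel test with no covariate or stratum named. Only the narrower statement, about the MMRMs, is true.

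The SAP's replacement of the protocol's CGI-S-adjusted GEE by that unadjusted comparison is a separate discrepancy and lends no weight to this point.

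**Conclusion.** The point holds as a low-cost improvement to one secondary analysis. CGI-I is the only secondary MMRM without a baseline covariate, and a suitable one is already scheduled for every subject and used by the protocol for the same scale. Its absence causes no bias and invalidates no planned result.

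The benefit is an SE smaller by about 0.5% to 4.6% if the correlation lies between 0.1 and 0.3, worth roughly 2 to 18 subjects on 180 (182 − 180 and 198 − 180), and essentially nothing at zero. A correlation of 0.5 would give more, but the documents offer no basis for assuming it. The gain is likely but not guaranteed.

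The change-score issue is one of wording. As the SAP stands, it could affect only descriptive output, and only if the protocol's general text is followed literally.

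**What to change.** 1. **SAP 7.4.7:** add baseline CGI-S as a covariate in the CGI-I MMRM, in the same form as the baseline term in the other secondary MMRMs.
2. **SAP 7.4.7, descriptive summaries:** state that CGI-I is summarized as observed scores or categories only, and that no change or percent change from baseline is computed for it. This overrides the general wording in the Protocol Synopsis, 9.1 and 9.3.3.2.

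The cost is one term in one model and one sentence. No new data are needed. CGI-S is also rated at screening, so the last pre-dose value can serve if the Visit 2 rating is missing, and few if any subjects should be lost from the model. Both edits belong before unblinding. If that has passed, report the adjusted CGI-I model as a labelled supportive analysis beside the planned one.
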